### **7.6.6 Malaria endemicity in the study area**

A malaria survey of schoolchildren will be conducted at approximately the same time as the cross-sectional surveys are undertaken in study children (November 2020 and November 2021) to assess the malaria parasite prevalence at the end of the transmission in the study areas and to monitor the trend in the distribution of molecular SP resistance markers. Two hundred randomly selected school children per country (total 400) aged 6-12 years resident in the study area who are well and have not received SMC will be tested for malaria by microscopy to assess the prevalence of malaria parasitaemia at the end of each malaria transmission season and to determine the overall level of malaria transmission and to assess the distribution of molecular markers of resistance to SP in the study area during the final period of the trial.

### **7.6.7 Drug resistance**

Dried blood spots from children who have malaria parasitaemia detected by microscopy at the final cross-sectional survey in November 2021 will be used for analysis of molecular markers of resistance to SP and AQ at MRTC, Bamako.

### **7.6.8 In vivo measurement of drug sensitivity to SP+AQ**

At the end of the 2021 malaria transmission season, an *in vivo* study will be done to determine whether the local strains of *P. falciparum* still remain sensitive to SP+AQ. At the time of the cross-sectional survey, a RDT for malaria will be done in addition to collection of blood slides and filter paper samples. Blood smears will be examined the same day, or as soon as possible afterwards, for any child who has a positive RDT test. Children who have microscopically-confirmed *P. falciparum* infection, but who are otherwise quite well, will receive a full treatment course of SP+AQ over three days, dosed according to age. Children will then be followed for 28 days according to a standard WHO treatment efficacy protocol, with parasitaemia and symptoms assessed at days 0, 1, 2, 4, 7, 14 and 28 after treatment. Children who have fever, a history of fever, or are unwell and who have a positive RDT will be treated with artemether-lumefantine. Infections occurring after day 7 (late parasitological failures) will be investigated to determine if the recurrent infection was due to a reinfection or a recrudescence using molecular markers.

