### **7.6.3 Prevalence of malaria parasitaemia and anaemia.**

A survey of all study children will be undertaken approximately one month after the last round of SMC administration at the end of each malaria transmission season. Temperature will be measured and any child who is febrile or who has other features suggestive of a diagnosis of malaria will have an RDT done; those who are positive will be treated with artemether/lumefantrine. Finger prick blood samples will be collected for preparing blood slides and filter paper blood spots. The prevalence of parasitaemia, including the presence of gametocytes, will be detected by microscopy.

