## Study outcomes

### Primary Endpoint

The primary end-point is the incidence of episodes of clinical malaria, as defined below, treated at a study health centre or hospital.

1.1 **Clinical malaria** is defined as an episode of fever (either measured axillary temperature  $\geq 37.5^{\circ}\text{C}$ , or a history of fever within the past 48 hours), and a positive blood film, with a *Plasmodium falciparum* parasite density of 5,000 per  $\mu\text{l}$  or more. This cut-off was used in the original three-year trial, as well as in previous studies of SMC in Burkina Faso and Mali, and in the phase 3 studies of the RTS,S/AS01 vaccine (1, 2, 5-7).

All passively-detected episodes of clinical malaria will be included in the analysis. Specifically, this includes visits to outpatient clinics and hospitals, as well as morbidity detected at the time of SMC or at the end of transmission season survey. These contacts can be considered 'passive' because the caregiver had to bring the child to the contact and because the SMC or survey was conducted at the health facility in many cases. As the focus is on passively detected cases, morbidity detected during home visits for serological sampling, and for the weekly parasitaemia survey (which was undertaken only in the initial phase of the study) are excluded. Morbidity detected at the time of vaccination is also excluded, because some children were visited at home and brought to the clinic in order to be vaccinated, so cases found at the time of vaccination cannot be regarded as passively detected.

To avoid double counting of disease episodes which result in more than one healthcare contact, episodes of the primary outcome documented within 7 days of a previous episode will not be counted. No adjustment is necessary to the person-time at risk (11).

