### **2.5 The treatment efficacy of the SP+AQ combination used for SMC**

- 2.5.1 The percentage of children with asymptomatic *P. falciparum* parasitaemia at the cross-sectional survey in November/December 2021, who, when treated with SP+AQ, have an adequate clinical and parasitological response (ACPR) after 28 days.

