#### **C) Study Year 5, to assess effectiveness of the seventh dose of RTS,S/AS01E (younger children only)**

Older children were not eligible for interventions in 2021. Consequently, this analysis will include only younger children, starting from 1st April 2021 until 31 March 2022 (i.e., covering the 2021 rainy season and subsequent dry season).

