## Analysis strategy

### Modified Intention to Treat

The primary analysis will be by modified intention to treat (mITT). The mITT population will include all children who were screened and who received the first dose of RTS,S/AS01E or control vaccine, irrespective of the number of doses of subsequent vaccines or SMC/SMC placebo received.

Children will contribute time at risk from the date of the first vaccination contact in 2017, until the end of the intervention period, which is either

- i) 31st March 2021, if born prior to 1st June 2016 (and thus over the age of five years in June 2021), or
- ii) 31st March, 2022, if born on or after 1st June 2016, and thus still under the age of five year in June 2021.

Prior to the end of the intervention period, children may be censored;

- 1) on the date last seen if lost-to-follow-up (LT FU),
- 2) on the date of permanent exit from the study area, or
- 3) on the date of death,

Children who temporarily left the study area with known exit and re-entry dates will have the corresponding person-time excluded from the analysis by intention to treat (and per protocol, if leaving the study area does not result in missed treatments).

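### The late-2021 in vivo drug study gives SP+AQ to parasitaemic trial children, some still at risk in Period C; the SAP has no rule for this and pools one ACPR over children with and without recent SP+AQ exposure

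*Combined protocol and SAP*

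**What the plan says.** **Who is treated.** Protocol 7.6.3: "A survey of all study children will be undertaken approximately one month after the last round of SMC administration". In the routine survey only febrile or symptomatic children are tested by RDT and treated. Protocol 7.6.8 adds, for 2021 only, RDT testing of surveyed children. Those with confirmed P. falciparum "but who are otherwise quite well, will receive a full treatment course of SP+AQ over three days, dosed according to age", and they are followed "with parasitaemia and symptoms assessed at days 0, 1, 2, 4, 7, 14 and 28 after treatment", which is six contacts after day 0. No arm or age restriction is stated. Protocol 10.3.3 sets an enrolment target of 155, apparently per country, and doubts that Mali can reach it.

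**Who is still at risk.** Under the SAP's analysis periods, older children leave Period A on 31 March 2021 and younger children on 31 March 2022. For Period C, which also ends on 31 March 2022, "this analysis will include only younger children".

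**What the SAP does about it.** Its rule begins "Prior to the end of the intervention period, children may be censored" and lists loss to follow-up, permanent exit and death; temporary absence is excluded from person-time. The covariates are country, age, sex and bednet use. None concerns SP+AQ given outside the allocation.

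**Contacts.** The Primary Endpoint section counts passively detected episodes, lists the included contacts, and excludes "morbidity detected during home visits for serological sampling, and for the weekly parasitaemia survey" and vaccination contacts. In vivo visits and the 7-day reaction visits (protocol 8.1) are not named.

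**The in vivo result.** SAP 2.5.1 is a single percentage: children with asymptomatic parasitaemia at the 2021 survey "who, when treated with SP+AQ, have an adequate clinical and parasitological response (ACPR) after 28 days".

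**The concern.** Treatment is triggered by parasitaemia, itself a secondary outcome (SAP 2.3.1). If one arm carries more infection in December, that arm receives more SP+AQ, and children in the RTS,S alone arm, allocated SMC placebo, receive active drug during their at-risk time. Any later cases averted would then be averted mostly in the less protected arm. That would bring the two arms closer, which is the favourable direction for the non-inferiority comparison. Period C is one of the three periods for which the SAP presents hypothesis tests, and it is where the seventh dose is judged.

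The ACPR raises a different issue. Protocol 7.6.8 asks whether local strains remain sensitive to SP+AQ. A parasite found about a month after an active SMC course has recently met the drug. One found in a child given placebo, or in an older child given nothing in 2021, has not. A single pooled percentage mixes the two.

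**Working it through.** **1. The plan's own in vivo figure (protocol 10.3.3).** n = z²p(1−p)/d² = 1.96² × 0.9 × 0.1 / 0.05² = 138.3, so 139. Then 139/(1 − 0.10) = 154.4, so 155. Both reproduce.

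**2. How many treated children are in Period C.**
- Younger share: 1 − 3860/5920 = 34.8% (SAP, Analyses in individual years), or 40% from the approximate 60% in protocol 7.6.9.
- If infection is similar by age, one target of 155 gives 54–62 younger children. Two targets (310) give 108–124, over three arms.

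**3. Denominators.**
- Period C: (2410 + 2624) × 0.348 / 3 ≈ 584 children per arm. At 200 per 1000 that is about 117 events, with SE(log HR) ≈ √(2/117) = 0.131.
- Period A: 6875 × 0.2 = 1375 events per arm, with SE ≈ 0.038.

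**4. Cases left after the survey.** Protocol 4.1 puts over 80% of cases in July–November, so under 20% fall in the other seven months. An even spread puts 4/7 of those in December–March: 0.2 × 0.20 × 4/7 = 0.023 cases per child. The ceiling, with all off-season cases after the survey, is 0.2 × 0.20 = 0.040.

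**5. Shift in the ratio** = (difference between two arms in children treated × later cases per child × relative risk of carriers) / arm events. SP+AQ is assumed to avert every later case, which overstates the effect.

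Assumptions not in the documents: a 2:1 prevalence ratio between the two arms with the third midway (shares 2 : 1 : 1.5, so difference = total/4.5), and carriers at 1 or 3 times the average risk.

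| Scenario | Difference treated | Events averted | Period C | Period A |
|---|---|---|---|---|
| Target kept, average risk | 54/4.5 = 12 to 124/4.5 = 28 | 0.3–1.1 | 0.2–0.9% | 0.02–0.08% |
| Target kept, 3× risk, ceiling | 28 | 3.3 | 2.8% | 0.24% |
| All treated, 30% v 15%, average risk | 584 × 0.15 = 88 | 2.0–3.5 | 1.7–3.0% | 0.15–0.25% |
| All treated, 30% v 15%, 3× risk, ceiling | 88 | 10.5 | 9.0% | 0.8% |
| Extreme: all 124 in one arm, 3× risk, ceiling | 124 | 14.9 | 12.7% | 1.1% |

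With the target kept but a 3:1 prevalence ratio, the 3× ceiling case gives 4.3% in Period C. In the fourth row, 30% prevalence at three times the average risk puts 90% of that arm's later cases in treated children, so that row is near its own limit.

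Applied to a true ratio of 1.20, a 2.8% shift gives 1.17 (about 0.2 SE) and a 9% shift gives 1.09 (about 0.7 SE).

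**6. Cross-check by another route, every carrier treated.** Observed ratio = 1.20 × (1 − s·e·f₁)/(1 − s·e·f₀), where f = p·r/(p·r + 1 − p). Assumed ranges: post-survey share s 8–20%, fraction of cases prevented e 40–80%, carrier relative risk r 2–4, prevalence p 20–40% (RTS,S alone) and 10–20% (SMC alone). The result is 1.115 to 1.200, at most 7% below 1.20. The 20% share is itself above what protocol 4.1 allows, because that remainder also covers April–June.

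**7. ACPR mix.** At equal prevalence, two-thirds of the younger 35–40% were allocated active SMC, so w = 23–27% of enrolled children. The pooled ACPR differs from the unexposed value by w × D, where D is the true difference between the strata. To reach the planned 5-point precision, D would have to be about 5/0.27 = 19 to 5/0.23 = 22 points.

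**The case against.** - **The primary analysis is not threatened.** A reader might infer that Period A is biased. The documents do not support that. By their own age split, 60–65% of children have left both periods, the rest are treated after the months holding over 80% of cases, and the shift is about 1% or less even in the extreme row. This stands.
- **Enrolment is capped.** Protocol 10.3.3 gives a target, and under it the Period C shift is small against an SE of 0.131. This stands as far as the target governs, but 7.6.8 reads as treating every eligible child, and the two sections are not reconciled.
- **Period C is imprecise anyway.** With a true HR of 1.0, the upper 95% limit is about exp(1.96 × 0.131) = 1.29 at 200 per 1000. At 305 per 1000 it is about 1.23. Both exceed 1.2, so a shift of 1–3% is unlikely to decide non-inferiority there. This stands.
- **Direction is not fixed.** It is tempting to say that the arms are pulled together. Extra treatment acts that way, but if morbidity found at in vivo visits were counted, detection would rise in the same, more infected arm and push the other way. The documents do not settle the net sign.
- **The contacts are largely covered already.** The SAP states which contacts count and requires passive detection, and scheduled in vivo visits do not fit. The reaction visits involve 50 children per arm per country, so they are balanced. Only a clarification remains.
- **The pooled ACPR is still informative.** It would go too far to say it cannot show whether strains remain sensitive. About three-quarters of enrolled children would be unexposed in 2021 (more if SMC lowers prevalence), and reinfection genotyping and resistance markers are planned. What remains is that the mix of exposures is known in advance and is not reported.

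**Conclusion.** The point holds in a limited form. Some younger children receive SP+AQ while at risk in Period C, selected on a state that the arms can affect, and the SAP has no rule for it. The treatment may move the Period C hazard ratio toward 1 by under about 3% with enrolment at target and a 2:1 prevalence ratio, and by up to about 9% if all carriers are treated. The larger figures need uncapped or extreme selection, three-fold risk, full protection to 31 March 2022 and the ceiling on later cases. Prevalence by arm in 2021 and the risk in carriers are assumptions; the documents give neither. The effect on Period A is negligible. A claim that non-inferiority is made easier overall is not supported, because the net direction is uncertain and the primary analysis barely moves.

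The single ACPR blurs the question about local strains without making it unanswerable. Both gaps are cheap to close before the code is broken.

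**What to change.** 1. **ACPR (SAP 2.5.1).** Report it overall and by 2021 SP+AQ exposure: younger children in the two active SMC arms, against RTS,S alone children and all older children. Cost: wider intervals. With 139 evaluable children, the exposed stratum would be about 32–37 (half-width about 10 points at 90% ACPR) and the unexposed about 102–107 (about 6 points).
2. **Period C sensitivity analysis.** End follow-up of all younger children, in every arm, at the start of the 2021 survey in that country. Censoring only treated children would select on parasitaemia and be informative. Cost: about four low-transmission months, or 13–23 of 117 events per arm (584 × 0.023 to 584 × 0.040), raising SE(log HR) from 0.131 to about 0.139–0.146. The main Period C analysis stays as planned.
3. **Tabulation.** Show in vivo participants by arm and age group, so that the size of the effect can be judged from data.
4. **Reconcile protocol 7.6.8 with 10.3.3** on whether all eligible children or a target number enter the in vivo study, and state the target per country or in total.
5. **Clarification only.** Name in vivo visits and 7-day reaction visits among the excluded active contacts in the SAP's Primary Endpoint section.

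The analysis and reporting changes require no change to treatment or visits.

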### **7.6.9 Investigation of possible rebound malaria**

Approximately 60% of trial children will, in line with national guidelines, not be eligible to receive SMC during the 2021 malaria transmission season as they will have reached the age of five years. These children may be at increased risk of malaria due to the fact that they have been partially protected from malaria during the first few years of their life. Employing the surveillance systems described in section 7.1, these children will be identified if admitted to hospital with severe malaria or when presenting to a clinic with proven uncomplicated malaria. Details of how this case control study will be undertaken will be provided in another proposal that will be submitted to the ethics committee in due course.

In order to investigate further the potential of four years of administration of SMC, seasonal vaccination with RTS,S/AS01E or both, antibodies against a range of malaria antigens will be measured in a finger-prick blood sample obtained from all study children at the start of the 2021 malaria transmission season and the patterns of response observed related to the risk of malaria in the subsequent malaria transmission season. At the same time a questionnaire will be administered which asks about risk factors for malaria that might confound analysis of the association between antibody pattern and risk. A second blood spot for antibody determination will be obtained at the time of the cross-sectional survey described in section 7.6.3 above.

Among children no longer eligible for SMC, the incidence rates of uncomplicated malaria and hospitalisation for malaria will be compared according to age, sex and prior adherence to study interventions (SMC history and vaccination history), to determine if children who have been well-protected during the study period have been placed at increased risk during the period after SMC and/or vaccination is stopped, a possibility that has been little investigated. To explore this issue further, we will develop case-control studies that will obtain information on additional relevant risk factors and potential confounders that are not routinely collected from all study children (e.g. measures of socio-economic status, housing construction, knowledge of malaria, use of LLIN, etc.) from cases of either uncomplicated or severe malaria and from controls sampled at random from the study cohort.

## **8. ASSESSMENT OF SAFETY**

### **8.1 Safety assessments**

Because there is no previous experience of the administration of sixth and seventh doses of RTS,S/AS01E, and to ensure there are no adverse outcomes following administration of a fifth dose of tetanus toxoid approximately 150 children in each country (50 in each intervention group) will be visited daily for seven days after their third and fourth booster doses and local and systemic side effects recorded. Additionally, the DSMB will undertake a safety review at the end of the 2020 malaria transmission season before progressing to the final year of the study.

Surveillance will be maintained throughout the study period for any SAEs. Any SAEs that are (a) considered by the investigators to likely to be linked to the administration of a study vaccine or study drug or (b) are suspected cases of meningitis or cerebral malaria or (c) are fatal or life threatening will be thoroughly investigated and reported to GSK and to the DSMB within 72 hours of their detection. All SAEs, whether considered related to the study interventions or not will be tabulated in a blinded fashion and provided to the DSMB and to GSK at the times requested by the DSMB. SAEs will be reported to the LSHTM ethics committee annually in a tabulated format. SUSARs will be reported to the sponsor and to LSHTM ethics committee within 72 hours of notification in a format similar to that outlined in LSHTM SOP 008. SAE's will be reported to the ethics committees in Burkina Faso and in Mali in line with their instructions following review of the protocol. Details of definitions of adverse events and SAEs and of reporting procedures are described in Appendix 2.

Experienced project staff based at the district hospitals are responsible for the identification of any child in the trial admitted to hospital and for ensuring their referral to a study physician. Hospital staff have been provided with additional training on the recognition of cases of meningitis, cerebral malaria or immune deficiency diseases and standard operating procedures have been developed for management of children suspected of having one of these conditions. The aetiology of cases of meningitis is determined by microscopical examination of cerebrospinal fluid samples for bacteria and white blood cells and by subsequent PCR testing at a reference laboratory. The death of any study child is investigated and, if this occurred in the community, a verbal autopsy will be done.

## **9. LABORATORY PROCEDURES**

### **9.1 Detection of malaria.**

A histidine rich protein (HRP2) based Rapid Diagnostic Test (RDT) will be used for the initial diagnosis of malaria and to guide treatment. All blood films will be read twice by two separate readers following the guidelines developed for the phase 3 RTS,S/AS01 trial [18]. Slides which are judged to be discordant for either positivity or parasite density will be read by a third reader. For slides with high or medium density parasitaemia ( $> 400$  parasites/ $\mu\text{L}$ ) readings are considered discordant if the higher count divided by the lower count is  $> 2$ . In the case of slides with low density parasitaemia ( $< 400/\mu\text{L}$ ), readings are considered discordant if the highest reading density is more than one  $\log_{10}$  higher than the lowest reading. In cases when one reader gives a count  $> 400/\mu\text{L}$  and the other  $< 400/\mu\text{L}$ , the second criterion will apply. For cases of discrepancy in definition of positivity/negativity, the majority decision is adopted. If the majority decision is positive, the final result is the geometrical mean of the two positive readings. In the case of discrepancies in parasite density, the final result is the geometric mean of the two geometrically closest readings.

## **9.2 Detection of markers of resistance to SP and AQ.**

Parasite DNA will be extracted from dried blood spots and nested PCR reactions will be used to detect the presence of mutations in the *dhfr* and *dhps* genes associated with resistance to pyrimethamine and sulphadoxine respectively, and the *pfCRT* and *pfMDR* mutations associated with resistance to amodiaquine [19-21]. PCR-RFLP will be used to detect the N511, C59R, S108N and I164L mutations in the *dhfr* gene, the A437G and K540E mutations in the *dhps* gene, the N86Y mutation in the *pfMDR1* gene and the K76T mutation in the *pfCRT* gene.

